9.3.4 Subgroups

The following subgroups, study size permitting, will be specified to identify subpopulations of interest and additional subgroups may be added if identified during the study conduct.

- Maternal age (<30 years; 30-<40 years; >40 years).

- Trimester of exposure
- Maternal autoimmune diseases [rheumatic diseases, systemic lupus erythematosus, inflammatory bowel disease, multiple sclerosis, type 1 diabetes]
- Indicators of immune suppression (if group size permits)
- Heterologous vaccine schedule (if group size permits)

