9.2.1 Inclusion Criteria

The study population will include all pregnancies, identifiable in the databases, ending in a live or still birth, a spontaneous abortion, an induced abortion, or an ectopic pregnancy, as identifiable in the participating databases during the study period. In Denmark and Norway, all

pregnancies ending in a live or still birth, as well as pregnancies leading to a hospital encounter due to termination will be identifiable. All pregnancies will be eligible for inclusion.

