9.7.1 Descriptive analyses

Counts and percentages will be presented for categorical variables (age at conception in categories, sex). Means, standard errors, medians and ranges will be presented for continuous variables (age at conception). The proportion of missing data will be described when appropriate. For maternal outcomes, pregnancy will be the unit of observation; for neonatal outcomes, a newborn will be the unit of observation. For the outcomes of congenital malformations and stillbirth the number at risk will be the total number of live or stillborn children.

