9.7.4 Subgroup analyses

All relevant analyses will be stratified by country, maternal age, sex, calendar time, trimester and seasonality if applicable and in subgroups specified in Section 9.3.4 where sample size permits.

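### As printed, the maternal age subgroups leave age 40 unassigned, which drops women aged 40 from the age strata if age is held in completed years

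*Protocol*

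**What the plan says.** Section 9.3.4 fixes the cut-points: "Maternal age (<30 years; 30-<40 years; >40 years". It makes the subgroups conditional on numbers: "The following subgroups, study size permitting, will be specified to identify subpopulations of interest and additional subgroups may be added if identified during the study".

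Section 9.7.4 puts them to use: "All relevant analyses will be stratified by country, maternal age, sex, calendar time, trimester and seasonality if applicable and in subgroups specified in Section 9.3.4", with the proviso that sample size must allow it. The first part of that sentence names maternal age without cut-points. The second part brings in the 9.3.4 subgroups. The 9.3.4 cut-points are the only ones for maternal age in the protocol.

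Eligibility has no age limit. Section 9.2.1 states "All pregnancies will be eligible for inclusion", and the exclusions in 9.2.2 do not mention age.

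Age appears in three other places, and none of them closes the gap:
- Section 9.7.1 ("Counts and percentages will be presented for categorical variables (age at conception in categories, sex") and the matching text in the abstract refer to age at conception in categories, without boundaries.
- Section 9.3.3 lists the woman's age as a covariate.
- Section 9.7.3 measures covariates with LMP as the anchor date.

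**The concern.** A set of age strata should place each eligible woman in exactly one group. Here one boundary value belongs to no group. If age is stored as a whole number of years, that value is a full year of age, and all of the women concerned belong to what was evidently meant to be the oldest group.

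Three things would follow. The stratum counts would not sum to the total. The oldest stratum would be less precise than the data allow. Because subgroup results are produced only where numbers suffice, and section 10 provides for masking of small counts (1 to 4 in most countries), a smaller stratum is also more likely to be suppressed.

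The protocol has fixed these cut-points and has not left them to the SAP. A SAP that repaired them would depart from the protocol text. Section 9.6 plans one common program for all data access providers, so a rule coded literally and not caught in verification would apply in each database.

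**Working it through.** There is no stated figure to reproduce. The check is whether the three intervals partition the age axis.

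**Inputs**
- Strata from 9.3.4: A is age < 30, B is 30 ≤ age < 40, C is age > 40.
- Eligible ages from 9.2.1 and 9.2.2: no limit. The check ran over ages 12 to 55.

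**Step 1, age in completed years.** Each whole-year age from 12 to 55 was assigned to A, B and C.
- Ages in no stratum: 40 only. It fails A (40 < 30), B (40 < 40) and C (40 > 40).
- Ages in more than one stratum: none.
- A recorded age of 40 covers every woman from her 40th birthday to the day before her 41st, so a full year of age is unassigned.

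**Step 2, exact age.** The same rule was applied to daily ages, in steps of 1/365 year, from 12 to just under 56. The only unassigned value is 40.0, that is, the birthday itself. A woman aged 40 and one day is in C.

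**Step 3, size of the loss.** Let f be the share of the intended oldest group (40 and over) whose recorded age is 40.
- In completed years, the oldest stratum keeps a fraction 1 − f. If exposed women and outcomes are lost in proportion, its standard error is multiplied by 1/√(1 − f).
- With exact age, f is close to 0 and the multiplier is close to 1.
- Table 2 gives births per database, but no table gives births by maternal age. Neither f nor a count of women lost can be obtained from the protocol.

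**Step 4, after the change.** With C as age ≥ 40, every whole-year age from 12 to 55 falls in exactly one stratum: 0 unassigned and 0 double-assigned. All cut-points are then whole years with the lower bound included, so completed years and exact age give the same assignment and the choice of unit no longer matters.

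**The case against.** The strongest reply is that nobody need be lost. The protocol treats age at conception as a continuous variable, with means and medians. Date of birth is described for Denmark and Norway and is used in the UK linkage, so exact age is obtainable there. Cut on exact age, the strata miss only women exactly on their 40th birthday. This stands, and it is why the loss is conditional. It does not remove the gap, because the protocol never says which unit will be used and completed years would be an ordinary choice.

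A second reply is that this is a typing slip. The form of the middle stratum implies that 40 belongs to the next one, and a greater-or-equal sign lost in conversion from PDF cannot be excluded. That also stands. If the signed protocol shows such a sign, nothing needs changing.

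A third reply is that verification of the common program should reveal unassigned women. It may well do so. Correcting the text beforehand is simpler.

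Three stronger readings are tempting, and the documents do not support them:
- A reader might infer that women aged 40 drop out of the study's analyses generally. Section 9.7.3 adjusts for measured covariates, age is one of them (9.3.3), and nothing ties that covariate to the three strata.
- A reader might bring in an age distribution from elsewhere and quote a number of births lost or a percentage loss of precision. The protocol gives no such distribution.
- A reader might call the oldest group the smallest or the one at highest risk. The protocol states neither.

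**Conclusion.** The point holds as a defect of wording with a conditional effect. As printed, the age subgroups in 9.3.4 do not cover age 40, and no other section assigns it.

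The loss runs from near zero, if exact age is used, to all women aged 40, if completed years are used. It can be narrowed no further from the protocol. It touches only the age-stratified and subgroup results, which are themselves subject to sample size. The main covariate-adjusted estimates, the eligibility rules and the study-size figures in Table 3 do not change.

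This rests on two assumptions: that the printed sign is the intended text, and that the age covariate in the main models is not coded with the same three strata. Severity is minor.

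**What to change.** In 9.3.4, change the top stratum from >40 years to ≥40 years, so that the strata read <30, 30-<40 and ≥40 years.

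In the same edit, name one reference date for maternal age and use it throughout. Section 9.7.1 speaks of age at conception and 9.7.3 anchors covariates at LMP. The sponsor should reconcile the two so that a woman near a boundary is classed the same way in the descriptive tables, the models and the subgroups.

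The cost is one symbol and one sentence. No new data or analysis is needed. Making the change before the common program is written avoids a later correction and rerun by the data access providers.

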9.4. Data sources

This study will be based on electronic routinely collected data in five European countries (listed alphabetically): Denmark, Italy, Norway, Spain, and the United Kingdom. Table 1 provides overview of the data sources in each country. All databases have access to birth registry and allow for mother-child linkage. Additional description of the participating data sources is provided in Annex 3.

Table 1 Summary of the data sources

Country	Denmark	Italy	Norway	Spain	UK
Data access provider	Aarhus University	ARS	University of Oslo	IDIAP	DSRU
Type of data	Record linkage	Record linkage	Record linkage	Record linkage & GP	GP medical record
Data source name	Danish registries	ARS	Norwegian registries	SIDIAP	CPRD
Size of data in 2019	5.7 M	3.5 M	5.4 M	5.8 M	16 M
Type of data					
Diagnosis coding	ICD-10	ICD-9CM/SNOMED	ICD-10CM/ICPC	ICD-10CM	ICD-10/READ/SNOMED
Hosp. discharge Dx	yes	Yes	yes	yes	yes
Date of death	yes	Yes	yes	yes	yes
Emergency unit visit Dx	yes	Yes	yes	yes	yes
Outpatient specialist visit Dx	Yes	No	yes	No./Yes referrals to specialists	yes
Primary care Dx	no	No	yes	yes	yes
COVID-testing	Yes	Yes (only positive results)	yes	yes	yes
Medicines dispensing outp.(pharmacy)	yes	Yes	yes	yes	no
Medicines inpatient	Some	Some	yes	no	no

Medicines prescribing	no	No	no	yes	yes
COVID-19 Vaccine brand	yes	Yes	yes	yes	yes
Mother-child linkage	yes	Yes- separate linkage	yes	yes	yes
Linkage to birth register	yes	Yes	yes	yes	Yes

9.5. Study size

Table 2 shows estimated number of live births expected annually from each participating database.

Table 2 Estimated annual number of live births in each participating country/database

	Denmark	Italy	Norway	Spain	UK
Live/still births, per year	60,000	25,000	60,000	45,000	10,000

In observational studies based on routinely collected data, where investigators do not control the study size, it is of interest to estimate the magnitude of an effect that can be ruled out with the available data and its precision.¹⁵ Specifically, of interest is the magnitude of the upper 95% confidence limit that can be ruled out for an outcome, given the estimated size of the exposed/comparator groups and expected prevalence of the outcome. As proposed by Rothman and Greenland, study precision is expressed “by designing a study that gives an upper limit for the confidence interval that has a specified probability of being below a chosen value. The multiplier Z [in the calculations] is derived from the desired confidence level: Z is the value of the standard normal distribution such that the area under the curve from $-Z$ to $+Z$ equals the confidence level. Z is 1.96 for 95% confidence.” (Rothman and Greenland, p. 600).¹⁵

Table 3 Upper limit of 95% confidence interval (CI) that can be ruled out with 80% and 90% probability under different assumptions regarding proportion of vaccinated births and prevalence of outcome

Example country	Total births	Spikevax exposed births	Example outcome	Allocation ratio	Outcome prevalence in exposed	Outcome prevalence in comparator	Upper 95% CI limit, that can be ruled out with 80% probability	Upper 95% CI limit, that can be ruled out with 90% probability
Denmark or Norway (largest number of births)	100,000	16667	Cardiac malformations	5	0.01	0.01	1.27	1.31
		16667	Any major malformation	5	0.05	0.05	1.11	1.13
		16667	Small for gestational age	5	0.1	0.1	1.07	1.09

	16667	Spontaneous abortion	5	0.2	0.2	1.05	1.06	
	9091	Cardiac malformations	10	0.01	0.01	1.36	1.43	
	9091	Any major malformation	10	0.05	0.05	1.14	1.17	
	9091	Small for gestational age	10	0.1	0.1	1.10	1.11	
	9091	Spontaneous abortion	10	0.2	0.2	1.06	1.07	
	4762	Cardiac malformations	20	0.01	0.01	1.51	1.61	
	4762	Any major malformation	20	0.05	0.05	1.20	1.23	
	4762	Small for gestational age	20	0.1	0.1	1.13	1.16	
	4762	Spontaneous abortion	20	0.2	0.2	1.09	1.10	
UK (smallest number of births)	20,000	3333	Cardiac malformations	5	0.01	0.01	1.70	1.84
		3333	Any major malformation	5	0.05	0.05	1.26	1.31
		3333	Small for gestational age	5	0.1	0.1	1.17	1.20
		3333	Spontaneous abortion	5	0.2	0.2	1.11	1.13
		1818	Cardiac malformations	10	0.01	0.01	1.99	2.21
		1818	Any major malformation	10	0.05	0.05	1.35	1.42
		1818	Small for gestational age	10	0.1	0.1	1.23	1.27
		1818	Spontaneous abortion	10	0.2	0.2	1.15	1.17
		952	Cardiac malformations	20	0.01	0.01	2.52	2.92
		952	Any major malformation	20	0.05	0.05	1.50	1.60
		952	Small for gestational age	20	0.1	0.1	1.32	1.38
		952	Spontaneous abortion	20	0.2	0.2	1.20	1.24
Assumption: true prevalence ratio = 1								

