Spikevax was authorised across the European Union (EU), following conditional marketing authorisation by the European Commission on 6 January 2021⁴ and was approved on 08 January 2021 by the United Kingdom (UK) Medicines and Healthcare products Regulatory Agency (MHRA).⁵ Currently, Spikevax is indicated for active immunisation to prevent COVID-19 caused by SARS-CoV-2 in individuals 18 years of age and older.¹ According to the 28 May update the UK Joint Committee on Vaccination and Immunisation recommends that is that COVID-19 vaccines should be offered to pregnant women at the same time as the rest of the population, in line with the age group roll out.⁶ At the same time, a multinational cohort study showed that COVID-19 infection in pregnancy was associated with increased in severe maternal morbidity and mortality and with neonatal complications.⁷ Thus, an uptake of COVID-19 vaccination among pregnant women should be expected. Indeed, as of 21 July 2021 the Danish Health Authority recommended vaccination of pregnant women in second or third trimester, citing similar recommendations in 20 countries. Vaccination of some or all pregnant women is recommended in Denmark⁸ and Spain, permitted in the UK, and permitted with qualifications in Italy, according to Covid-19 Maternal Immunization Tracker, provided by Johns Hopkins University.⁹

Use of COVID-19 Moderna Vaccine in pregnancy and its effect on the mother and the neonate are currently not fully understood.¹⁰ This postauthorisation safety study (PASS), aims to describe use of Spikevax use in pregnancy and to examine any potential association between Spikevax vaccination and pregnancy complications, and adverse pregnancy and neonatal outcomes. This study is a Category 3 Required Pharmacovigilance Activity in the RMP. Safety of the Spikevax in the general population is examined in a separate, dedicated PASS (reference number mRNA-1273-P904)

8. Research question and objectives

The overarching research question is: is there a greater risk or prevalence of pregnancy complications, adverse pregnancy outcomes, or adverse neonatal outcomes following pregnancies exposed to Spikevax compared with pregnancies unexposed to Spikevax?

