9.7.2 Measures of occurrence and measures of association

Prevalence of each outcome will be computed as number of observations with a given outcome divided by the total number of study population members. For neonatal death, a 28-day mortality risk will be the measure of occurrence among live-born infants. Prevalence/risks will be compared according to predefined exposure categories and using, whenever necessary,

plausible exposure risk windows. For example, for assessing the outcome of congenital malformations, births will be classified based on their exposure in the first trimester. For all other neonatal outcomes, exposure any time in pregnancy and per trimester may be considered.

Table 4 summarizes outcome-specific analysis populations and exposure windows.

Table 4 Summary of outcome-specific analysis populations and relevant exposure windows

Outcome	Analysis population	Relevant exposure window
Hypertensive disorders of pregnancy (preeclampsia, eclampsia, gestational hypertension)	All pregnancies	1st or 2nd trimester
Gestational diabetes	All pregnancies	1st or 2nd trimester
Bleeding during pregnancy	All pregnancies	1st or 2nd trimester
Postpartum haemorrhage	All pregnancies	Any time during pregnancy
Pregnancy-related death	All pregnancies	Any time during pregnancy
Fetal death (spontaneous abortion or stillbirth)	A combined population of stillbirths, livebirths, and pregnancies ending in a spontaneous abortion	Any time during pregnancy
Termination of pregnancy for fetal anomaly (TOPFA)	All pregnancies	Any time during pregnancy
Any elective pregnancy termination	All pregnancies	Any time during pregnancy
Ectopic pregnancy	All pregnancies	Any time during pregnancy
Fetal growth restriction/small for gestational age (SGA)	Live births	Any time during gestation
Preterm birth (<37 full gestational weeks)	Live births	Any time during gestation
Low birth weight (<2500 g)	Live births	Any time during gestation
Major congenital malformations	Live or stillbirths/TOPFA (whenever available) without evidence of teratogenic exposure or infection or chromosomal anomaly	First trimester
Microcephaly (based on head circumference)	Live births without evidence of teratogenic exposure or infection or chromosomal anomaly	Any time during gestation
Low 5-minute Apgar score	Live births	Any time during gestation
Neonatal death (death within 28 days of birth)	Live births	Any time during gestation

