9.7.3 Methods to control/assess confounding

Crude and adjusted measures of association will be computed comparing the exposed vs the unexposed (prevalence ratios, risk ratios, mortality rate ratios). Adjustment will be performed by the covariates measured, with LMP as the anchor date. Covariates will be included in the

appropriate regression model: log-binomial regression for prevalences and risks and Cox proportional-hazards regression for incidence rate ratios. Candidate covariates for inclusion in the analyses will vary by database. A propensity-score based adjustment may be considered and will be described in a separate Statistical Analysis Plan. Table 5 shows country-specific availability of the covariates.

Table 5 Proposed candidate covariates and data availability in participating databases

Variable/data type	AVAILABILITY OF DATA IN THE DATABASE (either via diagnosis code or procedure or treatment proxy)				
	DENMARK (NATIONAL REGISTRIES)	ITALY/ARS TOSCANA	NORWAY (NATIONAL REGISTRIES)	SPAIN/SIDIAP	UK/CPRD
Pregnancy feasibility counts for interim reports	Hospital-based ICD-10 codes for pregnancy related diagnoses or codes for prenatal visits from the Insurance registry for primary care prenatal visits	Hospital-based ICD-10 codes for pregnancy related diagnoses or codes for prenatal visits from the Insurance registry for primary care prenatal visits	All pregnancies in Norway that last at least 12 weeks are captured in the Medical Birth Registry of Norway (mandatory notification to the registry, 100% coverage)	Most pregnancies will be identifiable in primary care; some might be missed without linkage to hospital data	Pregnancy information will be available in the main primary care dataset following primary care and/or secondary care contact with the patient. This will be based on Read and/or SNOMED codes.
Country of residence	YES	YES	YES	YES	YES
Calendar year of delivery	YES	YES	YES	YES	YES
Pregnant woman's age	YES	YES	YES	YES	YES
Marital or cohabiting status	YES	To be verified	YES	To be verified	YES
Smoking	YES	To be verified	YES	YES	YES
Alcohol use (also ICD codes)	YES, IF BASED ON ICD CODES	YES	YES, IF BASED ON ICD CODES	To be verified	YES

Confidential

Post-marketing safety study for COVID-19 mRNA-1273 vaccine

Protocol mRNA-1273-P905, Date: 27 September 2021, Version 1.2

Marital status or other available socioeconomic measures	YES	YES	YES	YES Other available socioeconomic measures	YES
Gravidity	YES	YES	YES	YES	YES
Parity	YES	YES	YES	YES	YES

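### Table 3 counts all Spikevax-exposed births in the malformation rows, although only first-trimester exposure counts for malformations, so the stated malformation limits are too favourable by an amount that depends on an unstated share

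*Protocol*

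**What the plan says.** Protocol section 9.5 sets study size by precision. Table 3 lists, for an example country and outcome, the upper 95% limit for the prevalence ratio that can be "ruled out with 80% and 90% probability under different assumptions regarding proportion of vaccinated births and prevalence of outcome". Its inputs are "Z is 1.96 for 95% confidence" and "Assumption: true prevalence ratio = 1". Its group-size column is headed "Spikevax exposed births" and holds 16,667, 9,091 and 4,762 (of 100,000 births) and 3,333, 1,818 and 952 (of 20,000). Each count serves all four outcomes.

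The exposure windows are set elsewhere. Section 9.3.1 defines exposure in general as at least one dose during pregnancy. Table 4 gives SGA a window covering all of gestation and malformations the first trimester alone. The text of section 9.7.2 agrees: "for assessing the outcome of congenital malformations, births will be classified based on their exposure in the first trimester". Section 9.7.5 takes exposure in the second or third trimester, but not the first, as a negative control for malformations.

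No section states what share of exposed births is expected to be exposed in the first trimester.

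**The concern.** Within one scenario, the same number cannot be both the any-time count that SGA needs and the first-trimester count that malformations need, unless every exposed birth was exposed in the first trimester. The natural reading of the column is any-time exposure, and on that reading the malformation rows use too large an exposed group.

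Malformations are a named primary objective, and Table 3 is the protocol's statement of how much excess risk the study could exclude. Section 9.2 also allows the study period to be extended if the population is too small for specific outcomes. A reader who judged that from Table 3 would use the wrong count for malformations.

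**Working it through.** **Inputs from the protocol.** Z = 1.96; probabilities 80% and 90% (z = 0.842 and 1.282); true prevalence ratio 1; prevalence p = 0.01 (cardiac) or 0.05 (any major malformation); exposed count n1; comparator n0 = allocation ratio × n1.

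**Formula.** U = exp[(1.96 + z) × SE], with SE = √[((1 − p)/p) × (1/n1 + 1/n0)].

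**Reproducing Table 3.**
- Cardiac, n1 = 16,667, n0 = 83,335: SE = √[99 × (1/16,667 + 1/83,335)] = 0.0844. U(80%) = exp(2.802 × 0.0844) = 1.27 and U(90%) = exp(3.242 × 0.0844) = 1.31, as printed.
- Cardiac, n1 = 952, n0 = 19,040: SE = 0.3304. U = 2.52 and 2.92, as printed.
- All 24 rows agree to rounding in both columns when n1 is the full exposed count. The formula is sound, and the malformation rows contain no reduction for trimester.

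**Applying the protocol's own window.** Let f be the share of exposed births exposed in the first trimester. Replace n1 by f × n1 and leave n0 unchanged. The protocol does not give f, so the values below are assumptions. For orientation, section 9.3.1 makes the first trimester 98 days (LMP to LMP+97). With an assumed 280-day gestation and uniform timing of vaccination, that is 98/280 = 35%.

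Example: cardiac, f = 1/3, n1 = 5,556, n0 = 83,335 gives SE = 0.138 and U(80%) = exp(2.802 × 0.138) = 1.47.

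80% limits:

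| Row | Stated | f = 50% | f = 1/3 | f = 20% |
|---|---|---|---|---|
| Cardiac, 16,667 | 1.27 | 1.38 | 1.47 | 1.64 |
| Any major, 16,667 | 1.11 | 1.15 | 1.18 | 1.24 |
| Cardiac, 3,333 | 1.70 | 2.05 | 2.37 | 3.01 |
| Cardiac, 1,818 | 1.99 | 2.58 | 3.16 | 4.38 |
| Cardiac, 952 | 2.52 | 3.65 | 4.84 | 7.62 |
| Any major, 952 | 1.50 | 1.76 | 2.00 | 2.43 |

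Moving the later-exposed births into the comparator changes these limits by 0.01 or less.

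**Expected exposed cases in the 952 cardiac row.** 952 × 0.01 = 9.5 as printed. This falls to 4.8, 3.2 and 1.9 at the three shares, so the normal approximation is weak and the limits in that row are only indicative.

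**Two smaller checks.**
- The spontaneous-abortion rows apply a 20% prevalence to births. Table 4 uses stillbirths, live births and pregnancies ending in spontaneous abortion combined.
- Births per 1,000 people, from Table 2 ("Estimated annual number of live births in each participating country/database") over Table 1: Denmark 60,000/5.7 M = 10.5; Italy 25,000/3.5 M = 7.1; Norway 60,000/5.4 M = 11.1; Spain 45,000/5.8 M = 7.8; UK 10,000/16 M = 0.63.

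**The case against.** Table 3 is a grid of examples under varying assumptions, not a forecast, so different rows could be read for different outcomes. A reader who wants one third of 16,667 can go to the 4,762 row, which prints 1.51 against the recomputed 1.47. One third of 3,333 is near the 952 row, which prints 2.52 against 2.37. This stands in part. But section 9.5 gives no such instruction, the table varies the proportion vaccinated rather than the trimester, and nothing lies below the lowest rows.

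It is also fair that the limits are computed correctly from their inputs, that Table 3 is per database while section 9.7.6 foresees pooling, that section 9.3.2.1 makes organ-specific malformation analyses conditional on a signal in the composite, and that the extension clause in section 9.2 does not cite Table 3. These points limit the consequence but do not remove the mismatch.

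A reader might infer that precision in the small scenarios is overstated several-fold. The documents do not support that. The one pointer to a low first-trimester share is Danish: section 7 reports that by July 2021 "the Danish Health Authority recommended vaccination of pregnant women in second or third trimester". The largest inflation is in the UK rows, and for the UK the same section reports vaccination offered alongside the rest of the population, with no trimester limit. If the UK birth count is too low, those rows are too pessimistic on that account, which works in the opposite direction.

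A reader might also infer that Denmark and Norway cannot record spontaneous abortions well enough for those rows, since Table 5 says "All pregnancies in Norway that last at least 12 weeks are captured in the Medical Birth Registry of Norway". That entry describes feasibility counts for interim reports. Appendix 1 says the Danish hospital registry includes abortive outcomes, and section 9.9 already discloses undetected early losses. Only the denominator point remains.

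**Conclusion.** The concern holds as a mismatch of inputs: the malformation rows of Table 3 do not use the exposed group that the protocol will analyse, and the error is favourable for any first-trimester share below 100%.

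Its size rests on an assumed share. At one third, the distance of the limit from 1 on the log scale grows 1.6- to 1.7-fold in every scenario. The 80% limit itself grows 1.16-fold (16,667 row) to 1.92-fold (952 row) for cardiac malformations, and 1.07- to 1.33-fold for any major malformation. At one fifth, a three-fold increase appears only in the smallest cardiac row (7.62/2.52 = 3.0), where about two exposed cases are expected. A general claim of several-fold overstatement is not justified.

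The abortion denominator and the UK birth count are minor points that need reconciling. No exposure window or planned analysis is affected.

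**What to change.** - Recompute the malformation rows of Table 3 with first-trimester-exposed births, over a stated range of shares (for example one half, one third and one fifth of all exposed), and restate the limits.
- Flag rows in which the expected exposed cases are too few for the normal approximation.
- In section 9.2, say that for malformations the sufficiency of study size is judged on the first-trimester-exposed count.
- Minor: label and compute the spontaneous-abortion rows on the Table 4 population. Reconcile the UK figure of 10,000 births a year with the 16 M in Table 1, or say which subset it covers.

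The cost is recalculation of one table and a few sentences of text, with no extra data. The downside is that the stated precision for malformations becomes less favourable.
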